1.5. Study design

Prospective cohort study. Data will be collected at baseline through a questionnaire delivered at the general practice if the primary recruitment strategy will be applied. Otherwise, the baseline collection of the data will occur through a questionnaire home-mailed or delivered through a survey internet link if a strategy of recruitment through social media will be applied (please see section 2.7.2 for a description of the recruitment strategies). Outcomes will be collected by questionnaires either self-reported or parent-reported (collected through e-mail or text messages) at follow-up.

2. Methods

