2.3. Outcome measures

The primary outcome measure will be the recurrence/persistence of activity-limiting knee pain (i.e. yes/no pain that is limiting activities in the same knee) at 3-month follow-up⁴². Participants will also be asked about continuity of their knee pain (i.e. “how long have you been free of knee pain?”), to enable the distinction between recurrence (on/off knee pain episodes between baseline and follow-up) and persistence (continuous knee pain from baseline to follow-up) of knee pain. A secondary outcome measure that will be collected is the recurrence/persistence of activity-limiting knee pain at 6-month follow-up.

Previous studies have shown an effect of the treatment received on the change in risk group for the recurrence/persistence of pediatric pain⁴³ and on the change in pain and function⁴⁴. Therefore, an additional outcome measure that might potentially be assessed include the treatment effectiveness on the recurrence/persistence of knee pain (provided that there will be the possibility to collect data on the treatment given). For practical reasons, it might be considered assessing this additional outcome on a subsample of children and adolescents.

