3. Har du ondt i det ene knæ eller begge knæ?	 Kun det ene knæ (højre knæ)  Kun det ene knæ (venstre knæ)  Begge knæ
4. Hvor lang tid har du haft ondt i knæet? Hvis du har ondt i begge knæ skal du svare ud fra det knæ hvor smerterne har varet længst	 under 3 måneder  3–6 måneder  6–12 måneder  mere end 12 måneder (hvor mange år? _____)
5. Hvordan startede dine knæsmerter? Hvis du har ondt i begge knæ skal du svare ud fra det knæ hvor smerterne har varet længst	 Kom pludseligt (f.eks. da jeg fik en skade)  Kom gradvist (f.eks. langsomt over en længere periode)
6. Hvor ofte oplever du dine knæsmerter? Hvis du har ondt i begge knæ skal du svare ud fra det knæ hvor smerterne har varet længst	 Sjældent  Månedligt  Ugentligt  Mere end en gang om ugen  Næsten dagligt
7. Har du ondt andre steder i kroppen som gør at du ikke kan deltage i dine normale aktiviteter (leg i skolegården, sport og lignende)? I dette spørgsmål menes andre steder end knæet	 Nej  Ja. Marker venligst hvor. Du må gerne afkrydse mere end et område:  Hovedet  Ryg eller nakke  Skulder  Albuen  Håndled eller hånden  Underbenet  Låret  Bækkens (badebuksområdet)  Ankel, hælen eller fodden  Andet (_____)

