8. Calculation of the 3-month and 6-month knee pain prognosis stratified by treatment received and baseline prognostic risk group, provided that data on the treatment given to the patients can be collected. Alternatively, instead of stratifying the analysis by treatment, analysis can be adjusted by treatment received.

In addition, potential changes of the risk groups at 3-month follow-up depending on the treatment received might be calculated provided that the prognostic tool is delivered at the 3-month follow-up as well. In this way it might be possible to track the effectiveness of the treatment and if it resulted in a change of risk group.

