2.14. Impact/dissemination

The present study will provide data on the prognosis for knee pain in children and adolescents who present to primary care. In addition, this study will provide data on the usability of a prognostic tool to allocate children and adolescents to a category of risk for knee pain recurrence and consequently provide them with the best targeted treatment. The study results will be disseminated at scientific conferences and through appropriate scientific journals. In addition, general practitioners, children and parents participating into the study will be regularly provided with feedback about the ongoing study.

Examples of papers that might be developed from this study (provisional names are provided):

- 1) The Adolescent Knee Pain (AK-Pain) prognostic tool: protocol for a prospective cohort study
- 2) Stability of prognostic factors for knee pain collected with a questionnaire in general practice
- 3) The development of a prognostic tool for knee pain in children and adolescents in general practice
- 4) Effect on the treatment delivered on the knee pain prognosis on a subsample of the participants recruited in the AK-pain project

3. Protocol amendments

Potential protocol amendments might occur during the prognostic tool piloting and development stage. Protocol amendments will be disseminated to proper scientific journals.

4. Declaration of interest

The study's investigators have no conflicts of interest to declare.

5. Access to data

The final dataset will be accessed by [name], [name], [name] and [name].

References

doi:10.1177/0363546515622456
3. Houghton KM. Review for the generalist: Evaluation of anterior knee pain. *Pediatr Rheumatol.* 2007;5:1-10. doi:10.1186/1546-0096-5-8
5. Rathleff MS. Patellofemoral pain during adolescence: Much more prevalent than appreciated. *Br J Sports Med.* 2016;50(14):831-832. doi:10.1136/bjsports-2016-096328

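### Optional treatment analyses in a non-randomised cohort are worded as showing treatment effectiveness, which neither risk-group stratification nor change of risk group can establish

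*Combined protocol and SAP*

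**What the plan says.** Section 1.5 describes the design as a "Prospective cohort study". No treatment is allocated, and section 1.1 notes that the treatment given for knee pain in this age group varies with the underlying condition.

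Treatment appears in three later places:

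- **Section 2.3:** "an additional outcome measure that might potentially be assessed include the treatment effectiveness on the recurrence/persistence of knee pain", but only "provided that there will be the possibility to collect data on the treatment given". The section also allows a restriction to part of the cohort: "it might be considered assessing this additional outcome on a subsample of children and adolescents".
- **Section 2.10:** Step 8 is the "Calculation of the 3-month and 6-month knee pain prognosis stratified by treatment received and baseline prognostic risk group", if treatment data can be collected, with adjustment for treatment received as the alternative. The paragraph after it adds that changes of risk group at 3 months, according to treatment received, might be calculated if the tool is given again. It then says that in this way "it might be possible to track the effectiveness of the treatment and if it resulted in a change of risk group".
- **Section 2.14:** The fourth provisional paper title is "Effect on the treatment delivered on the knee pain prognosis on a subsample of the participants recruited in the AK-pain project".

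Section 2.10 names no confounder for these analyses other than the baseline risk group. It has no provision for regression to the mean or natural recovery, and no caution about causal interpretation.

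**The concern.** Step 8 itself is worded descriptively. The sentence on tracking effectiveness, the outcome in 2.3 and the paper title are not: they attribute differences, or a move between risk groups, to treatment. Three features of the study work against that reading.

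1. Treatment that depends on the child's condition or severity brings a difference in prognosis with it.
2. Three risk groups built on an imperfect score cannot remove all of that difference.
3. Children placed in an extreme group by a noisy score tend to move towards the middle on repeat measurement, whatever is done for them.

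If the optional analyses were carried out and reported in the words used, a treatment could be said to work, or to harm, on data that cannot show either. The direction of the error is not fixed in advance, so a reader could not allow for it.

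**Working it through.** **The plan's own figures.** The documents give no effect size, power or sample size for any treatment comparison. The only related figures are for recruitment, and they reproduce: 168 × 5000 × 0.20 × 0.0119 × 0.5 × 0.30 = 299.9, stated as 300. For the smaller target, 100/3 = 33 per risk group, against approximately 30 in section 2.5. That makes equal thirds a reasonable working assumption, although section 2.10 step 5 will set the cut-offs from ROC curves.

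**Inputs not in the documents.** Test-retest reliability (section 2.8.7 reports a pilot but no coefficient), the strength of treatment selection and the strength of prognosis are all assumed below. The true treatment effect is zero throughout. Checks 1, 2 and 4 used 1,000,000 simulated children per scenario.

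**1. Outcome comparison, as in step 8.** Severity S is standard normal. The tool score is T = √rel × S + √(1 − rel) × noise. The log-odds of treatment are g × S and of persistent pain b × S. Risk groups are thirds of T. The entries are treated minus untreated risk of persistent pain, in percentage points; the within-group value is the mean over the three groups.

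| b | g | Crude | Within groups, rel 0.5 | rel 0.7 | rel 0.9 | rel 1.0 |
|---|---|---|---|---|---|---|
| 0.7 | 0.5 | 7.3 to 7.6 | 4.4 | 3.3 | 2.2 | 1.5 |
| 0.7 | 1.0 | 13.0 to 13.3 | 8.3 | 6.1 | 4.0 | 2.4 |
| 1.0 | 0.5 | 9.9 to 10.0 | 6.1 | 4.5 | 2.7 | 1.8 |
| 1.0 | 1.0 | 17.1 to 17.5 | 11.2 | 8.2 | 4.6 | 3.2 |

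Stratification helps but does not remove the bias. Some remains even with a perfectly reliable score, because three groups are coarse. The sign makes treatment look harmful.

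**2. Change of risk group, treated against untreated, not stratified by baseline.** Here the log-odds of treatment are 1.0 per SD of the observed baseline score, and the repeat score correlates r with the first. The share moving to a lower risk group is:

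- r = 0.5: 32% treated, 19% untreated
- r = 0.7: 25% treated, 17% untreated
- r = 0.9: 15% treated, 11% untreated

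Treatment now looks beneficial. Within the baseline high group alone the sign reverses: at r = 0.7, 33% of treated and 39% of untreated children leave it. If treatment follows true severity and not the noise in the score, the unstratified comparison shows no difference (21% in each at reliability 0.7). Within the high group, however, 29% of treated and 46% of untreated children leave it (g = 1.0).

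**3. Change of risk group read as before and after.** With c the upper-third cut of a standard normal score, P(second score ≤ c | first score > c) is 40%, 34%, 28% and about 20% for r = 0.6, 0.7, 0.8 and 0.9. That share leaves the high group with no effect of anything.

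**4. Items of the tool.** Sex, mode of onset and parental pain cannot be expected to respond to treatment of the child. With r = 0.6 for the remaining items, if fixed items hold 0, 25, 50 or 75% of score variance:

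- The share leaving the high group with no effect is 40, 35, 28 and 20%.
- The extra share leaving under a real improvement of 0.5 SD in the changeable part falls from 23 points (0% fixed) to 14 points (75% fixed).

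Fixed items therefore hide change. Pain duration (item 4, "Hvor lang tid har du haft ondt i knæet") behaves differently. A child in the lowest category, under 3 months, whose pain continues must be in a higher category by the 3-month follow-up, and a recovered child has no answer that fits.

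**The case against.** The strongest reply is that little of this is committed. The wording in 2.3 and 2.10 is conditional, the paper titles are provisional, and neither the aim in 1.2 nor the objectives in 1.4 include a treatment effect. The follow-up questionnaire outlined in 2.8.2 mentions neither treatment nor a repeat of the tool. Step 8 already stratifies by baseline risk group and speaks of prognosis, not effect. All of this stands, and it limits how serious the point is. It does not answer it: if the analyses are done, this text is the only guidance on how to read them.

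Four stronger readings are tempting, and the documents do not support them.

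- **That step 8 would produce a large spurious odds ratio.** Take two equal groups with risks of 60% and 20%, treated 60% and 20% of the time. Crude risk is (0.6 × 0.6 + 0.2 × 0.2)/0.8 = 50% in the treated and (0.4 × 0.6 + 0.8 × 0.2)/1.2 = 33% in the untreated, an odds ratio of 2.0. That is an unstratified comparison. If the two groups are the risk groups, stratifying as step 8 does returns an odds ratio of 1.0.
- **That the 20% to 40% movement is a bias between treatments.** The paragraph describes change according to treatment received. Regression to the mean is common to all treatments unless treatment choice depends on the baseline state. The figure applies only to an uncontrolled before-after reading.
- **That unchangeable items create apparent effects.** They damp movement. Pain duration can force a move upwards, but nothing shows that this would differ by treatment, and the item weights are not yet set.
- **That the prognostic tool is compromised.** Scores and cut-offs come from steps 3 to 5; step 8 takes the risk group as given.

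**Conclusion.** The concern holds in a limited form. Conditional analyses of a non-randomised cohort are given a causal reading in 2.10, 2.3 and 2.14, and the design cannot support it. With no true effect, stratifying by risk group reduces a spurious difference of about 7 to 17.5 points to about 1.5 to 11 points. Change of risk group compared without regard to baseline can favour the treated (25% v 17% at r = 0.7) when treatment follows the observed score. The bias can therefore run in either direction.

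These sizes rest on assumed reliability, selection and prognostic strength and on equal-thirds risk groups; they show that the mechanism matters, not what this study would find. That treatment follows condition or severity is inferred from the general statement in 1.1; the plan does not say how treatment will be chosen in this cohort. The primary outcome, the development of the tool and its accuracy analyses are unaffected. Severity is minor.

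**What to change.** 1. In 2.10, delete the sentence saying that change of risk group tracks the effectiveness of treatment.
2. In 2.3 and in the fourth paper title, replace the effectiveness and effect wording with prognosis described by treatment received. Step 8 already reads this way and needs no rewording.
3. If change of risk group is reported, present it descriptively and within baseline risk group. Note that movement is expected without any treatment effect, that fixed items limit it, and that pain duration can only rise while pain lasts.
4. If a treatment association is shown, adjust for the continuous baseline tool score, which avoids the coarseness of three groups. State that the result is non-causal: an imperfect score leaves confounding by severity, and the tool records no diagnosis, so confounding by diagnosis remains.

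The cost is a few sentences and one covariate that is already collected. No data are needed beyond the treatment data, and the repeat of the tool, on which the plan already makes these analyses conditional. The drawback is that the optional paper becomes descriptive.

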2.11. Full analysis set

In order to obtain a “full analysis set” for the project, participants will have to provide data from baseline through the 3-month and 6-month follow-up, which will allow to estimate the short-term and long-term knee pain prognosis. Please refer to figure 4 for a description of the full analysis set. Data completeness (i.e. completion and accuracy of data forms) will be monitored and actions will be taken to overcome potential problems such as missing data ⁵¹. In case of missing data, the missing observation will be replaced by means of an imputation process (e.g. multiple imputation by chained equation) depending on the number of missing observations for the follow-up stages (i.e. multiple imputation is usually performed when the percentage of missing data is low). A sensitivity analysis will also be carried out in order to compare results between the analysis carried out on the dataset with missing observation (complete-case analysis) and the multiple imputed dataset (multiple imputation analysis). A backup copying of the dataset will be performed daily.

Figure 4. Complete-case and multiple imputed data

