2.10. Analysis plan

The analysis plan that will lead to the development of the final prognostic tool will include the following stages:

1. Descriptive analysis of the collected data. Results will be presented as means with SDs and as percentages.
2. Assessment of potential floor and ceiling effects of the items included in the prognostic tool. This will be done by checking that for those items that represent an ordinal or categorical variable with more than two potential response categories, the responses given are not skewed towards the top or bottom extreme of the scales (e.g. a ceiling or floor effect is present if >15% of the respondents report the lowest/highest score of the scale ^{42,45,57}).
3. Estimation of knee pain prognosis (i.e. recurrence/persistence of knee pain, dichotomous outcome) at 3-month and 6-month follow-up by means of multiple logistic regression to estimate ORs and 95% confidence intervals for each item included in the tool. This will inform on which factors are most related to the prognosis of knee pain and will provide an insight on the scores of the prognostic tool (both overall and for subscales) to be applied for the creation of the initial risk groups. Alternatively, the RR will be estimated if a general linear model analysis will be carried out.
4. Discriminant validity of the prognostic score will be assessed by using receiver operating characteristics (ROC) curves and by calculating the area under the curve (AUC) for the overall score and subscales of the prognostic tool.

[figure not shown]
5. Creation of risk groups for the recurrence/persistence of knee pain on the basis of cut-off scores identified using the ROC curves for the overall tool score. The initial idea is to have three risk groups (low/medium/high), which have to be clinically meaningful. More importance will be given to the sensitivity of the tool over the specificity.
6. Assessment of the predictive ability of the risk groups defined at baseline by calculating the sensitivity, specificity and negative and positive likelihood ratios (LRs) against the primary and secondary outcome (i.e. 3-month and 6-month recurrence/persistence of knee pain; disability/activities limitation due to knee pain).
7. Assessment of the potential influence of non-modifiable patients' characteristics on the predictive ability of the risk groups defined at baseline by stratifying the former analysis by age groups and sex.

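### Agreement between complete-case and imputed results, the only missing-data check in section 2.11, is not evidence against loss that depends on the child's outcome

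*Combined protocol and SAP*

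**What the plan says.** Section 2.11 defines the full analysis set as children with data at every stage: "participants will have to provide data from baseline through the 3-month and 6-month follow-up". For missing data, "the missing observation will be replaced by means of an imputation process (e.g. multiple imputation by chained equation"). Whether this is done is left open, "depending on the number of missing observations for the follow-up stages", with a remark that multiple imputation is usually done when little is missing. The one missing-data sensitivity analysis is described as "A sensitivity analysis will also be carried out in order to compare results between the analysis carried out on the dataset with missing observation" (complete cases) and the imputed dataset. The plan states no missingness assumption, no imputation model and no analysis that lets non-responders differ from responders.

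The results at stake are in section 2.10:
- step 3: "multiple logistic regression to estimate ORs and 95% confidence intervals for each item included in the tool", with a risk ratio as an alternative;
- step 4: "calculating the area under the curve (AUC) for the overall score and subscales of the prognostic tool";
- step 5: cut-offs and risk groups;
- step 6: "calculating the sensitivity, specificity and negative and positive likelihood ratios (LRs) against the primary and secondary outcome";
- step 8: prognosis by baseline risk group and treatment, if treatment data can be collected.

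The only other sensitivity analysis, in section 2.5, compares recruitment sources. Section 2.8.3 collects reasons for loss to follow-up but gives them no role in the analysis.

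**The concern.** The tool items are collected at baseline and the yes/no outcome later by e-mail or text, so the outcome is the value most likely to be missing. Imputing a missing outcome from the tool items means drawing it from the logistic model fitted to the responders. Refitting that model to the completed data returns nearly the same coefficients, whatever caused the loss. A comparison that gives the same answer under harmless and harmful loss cannot tell them apart on those measures.

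The harmful pattern is plausible. For example, children who have recovered may stop replying, and more often if their baseline problem was mild. The item weights, cut-offs and low-risk label would then come from a distorted sample, and the planned check would appear to support them.

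**Working it through.** **Inputs.** N = 300 is the baseline target in section 2.5, and the plan's figure reproduces: 168 × 5000 × 0.20 × 119/10,000 × 0.5 × 0.30 = 299.9. The outcome rate is assumed to be 50%; the only background figure, in section 1.1, is about 50% with knee pain at 1 or 2 years. The documents give no loss rate or loss mechanism, so every follow-up probability below is an assumption.

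**Step 1: hand calculation.** Take a score cut with sensitivity 0.76 and specificity 0.52. Of 150 children with the outcome, 114 score high and 36 low. Of 150 without it, 72 score high and 78 low. The true high-versus-low OR is (114 × 78)/(72 × 36) = 3.43, and the low-score group's risk is 36/114 = 32%.

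Among responders, this OR is multiplied by (f_high,yes × f_low,no)/(f_high,no × f_low,yes), where f is the probability of follow-up by score group and outcome. Imputation within score group gives non-responders the responders' risk, so it returns the same OR.

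- (a) Follow-up 0.90 with the outcome, 0.60 without. Factor (0.90 × 0.60)/(0.60 × 0.90) = 1.
- (b) Follow-up 0.90 with the outcome; without it, 0.80 high score and 0.45 low score. Factor (0.90 × 0.45)/(0.80 × 0.90) = 0.5625.
- (c) With the outcome, 0.90 high score and 0.60 low score; without it, 0.85. Factor (0.90 × 0.85)/(0.85 × 0.60) = 1.5.

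| | Loss | OR, both analyses (true 3.43) | Low-score risk, both (true 32%) | Sensitivity, complete / imputed (true 0.76) | Specificity, complete / imputed (true 0.52) |
|---|---|---|---|---|---|
| (a) | 25% | 3.43 | 32.4/79.2 = 41% | 0.76 / 0.74 | 0.52 / 0.55 |
| (b) | 24% | 1.93 | 32.4/67.5 = 48% | 0.76 / 0.69 | 0.38 / 0.47 |
| (c) | 16% | 5.15 | 21.6/87.9 = 25% | 0.83 / 0.81 | 0.52 / 0.55 |

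In (a) the overall outcome rate is 50% in truth, 60% in complete cases and 59% after imputation. If step 3's alternative risk ratio were used, (a) would also bias it: the true value is (114/186)/(36/114) = 1.94, against (102.6/145.8)/(32.4/79.2) = 1.72 in both analyses.

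**Step 2: simulation with a continuous score.** 1000 cohorts of 300 per scenario, logit P(Y=1) = 0.8X with X standard normal, and 20 imputations of Y from X. Mean values, full data / complete cases / imputed:
- random loss: log OR 0.815 / 0.818 / 0.818;
- (a): log OR 0.814 / 0.815 / 0.813; AUC 0.702 / 0.702 / 0.702;
- (b): log OR 0.815 / 0.585 / 0.584; AUC 0.702 / 0.643 / 0.648;
- (c): log OR 0.807 / 0.985 / 0.986; AUC 0.701 / 0.735 / 0.736.

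The mean gap between the two analyses in log OR is 0.002 or less in every scenario. A separate simulation with three predictors and 30% loss gave the same pattern. At n = 300 its mean absolute gap in log OR was about 0.026 (sampling SD about 0.18), whether loss was random or depended on the outcome.

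**Step 3: help from the other time point.** In the three-predictor simulation, loss was made to depend on outcome and predictor jointly. Half of those lost at 3 months then answered at 6 months, and imputation used that answer. The OR was 1.73 imputed and 1.70 in complete cases, against a true 2.22.

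**Step 4: does a shifted imputation work?** The true differences in log-odds between non-responders and responders are:
- (a): ln[(0.10/0.40)/(0.90/0.60)] = -1.8 in both score groups;
- (b), low score: ln[(0.10/0.55)/(0.90/0.45)] = -2.4; high score: ln[(0.10/0.20)/(0.90/0.80)] = -0.8;
- (c), low score: ln[(0.40/0.15)/(0.60/0.85)] = +1.3; high score: ln[(0.10/0.15)/(0.90/0.85)] = -0.5.

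Applying score-specific shifts recovered log ORs of 0.82 in (b) and 0.81 in (c). A constant shift is not enough. In the three-predictor joint-loss case, constant shifts from -0.5 to -2 left the OR at 1.71-1.76 against a true 2.23, while a shift of -1.1 with a slope of +1.0 on the predictor returned 2.23.

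**The case against.** A reader might infer that agreement between the two analyses always hides bias, or that the comparison can never show outcome-dependent loss. The documents support neither reading.

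- If loss depends on the outcome alone, as in (a), the ORs and AUC agree because both are right. Only absolute risk is wrong, and risk by group is a step 8 result that depends on treatment data.
- Section 2.11's full analysis set requires both follow-ups. On that definition, complete cases drop a child who answered at 3 months but not at 6, while imputation keeps the observed 3-month outcome. With scenario (b) applied as 6-month loss after 5% random loss at 3 months (500 cohorts of 300), the 3-month log OR was 0.823 full, 0.592 complete-case and 0.822 imputed. The check exposes that loss, and imputation is right.
- The two analyses can differ in sensitivity and specificity, so score-dependent loss can show there. Such a gap does not vindicate imputation, however: in (b) imputation misses both true values.
- The imputation model is left open, and follow-up asks how long the child has been free of knee pain. A 6-month answer to that question bears on 3-month status and was not modelled here. It cannot help for children lost at both points.
- The second cinema ticket (section 2.7.3) and two reminders (section 2.8.2) may keep loss low. With scenario (b) scaled to about 10% loss, the log OR is 0.74 against 0.81, within half a sampling SD (0.14); at 5% loss it is 0.78.

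These points limit the reach and size of the problem. They do not remove it, because incentives cannot show that the remaining loss is ignorable.

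**Conclusion.** The concern holds in a limited form. For children without the outcome being analysed, chiefly those lost at both follow-ups, agreement between complete cases and multiple imputation is uninformative about outcome-dependent loss. Under joint dependence on outcome and score, both can understate or overstate the tool's discrimination by similar amounts: AUC 0.64-0.65 or 0.74, against a true 0.70, at 16-24% assumed loss. Under outcome-only loss the error is in absolute risk. These sizes rest on assumed loss rates, loss mechanisms and a 50% outcome rate, and they shrink quickly as loss falls. This is an inexpensive improvement to the analysis plan; it does not show that the results will be biased.

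**What to change.** In section 2.11:

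1. Keep the complete-case versus imputation comparison, and state that agreement does not test outcome-dependent loss among children without the outcome.
2. Add a delta-adjusted multiple imputation of the 3-month and 6-month outcomes, using observed answers from the other time point as auxiliary data.
3. Apply a constant shift and also a shift that differs by baseline tool score. Use a split fixed before the risk groups are derived, for example below versus above the median of a provisional score, so that it does not depend on the step 5 cut-offs.
4. State the grid of log-odds shifts in advance (for example -2.5 to +2.5, odds ratios of about 0.08 to 12). Label its width an assumption, and judge plausible values against the reasons for loss collected under section 2.8.3.
5. Repeat steps 3-6, and step 8 if it is done. Report the range of the ORs, AUC, sensitivity, specificity and risk per group, and the shift at which the cut-off or the low-risk conclusion changes.

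The cost is a few sentences and extra runs of the imputation code, with no new data or participants. The downside is a wider, less favourable stated range for the tool's performance.
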